## 18.0 Confidentiality of Data

1. To maintain the confidentiality of the data:

- I will use a unique study identifier to code individuals' identifiable data and will store the master list separate from the study data.
- I will use a unique study identifier to code individuals' data, but it will never be linked to a master list.
- Other- please explain: Utilization data collected from the NeuViCare app will be manually entered into study survey linked with individual contact information. The PI will, using the study key, merge data on app utilization with study data to examine "exposure" to the intervention prior to analysis. Aggregate deidentified data about questions asked to the conversational AI assistant will be shared by Amicus Brain by email. By limiting who has access to utilization data from NeuViCare, reporting questions to NeuViCare in aggregate, and storing data in secure locations, we will protect participant confidentiality. Caregivers who participate in the CONFIDENCE will be notified that their app utilization data will be recorded.

Provide a plan to maintain or destroy identifiers once analysis of identifiable information is complete. All identifiers will be removed by the PI from study data prior to long-term storage in an encrypted Box folder. For survey data, this will be done first by downloading data in REDCap using the "Remove Identifiers" function, followed by visual examination to confirm all variables with identifying information is removed. Columns in Eventbrite (e.g., email addresses) will be manually deleted prior to saving. The electronic study key will be deleted.

- I attest that any recordings (audio or video) saved to a portable device will be deleted by formatting the device's storage memory.

How are you storing your electronic data?

- CWRU Redcap
- CWRU Secure Research Environment (SRE)
- CWRU Box
- OnCore
- CWRU Secure Network Drive
- Zoom Cloud
- Portable device (must be encrypted, not just password protected)
- Other - List storage method and provide justification: Downloaded data is stored in Box on portable devices, rather than in less secure locations (e.g., Documents or Desktop). Eventbrite information on program registrations is maintained by USC; USC will share login information with the PI so she can manually download data on registrants for analysis to reduce the need for data transferring by email. Intervention recordings will be temporarily stored in a Case Western's Box drive with limited access while the study team checks for fidelity, and then deleted at the end of this research study. Electronic data on caregiver utilization of the NeuViCare app is maintained by Amicus Brain in a HIPAA compliant Google Drive Folder. The PI will have access to user data via a dashboard with a unique

login. See attached NeuViCare security information.

*Please note: if you're storing or entering your electronic data in any system other than an approved system listed above, please contact the CWRU IRB ([[contact]](mailto:[contact])).*

2.  I acknowledge that paper research data and documents will be stored in a double-locked secure environment in the following **location**: Click here to enter text.  
 We will not have paper research documents.
3. Will data be shared?  
 Yes
  - List the exact data elements that will be shared: De-identified survey data from the surveys will be shared, as well as de-identified qualitative interview transcripts with investigators at the University of Southern California, led by [name], who co-developed CONFIDENCE with the PI. The Case Western study team will also provide "over the shoulder" (i.e., Zoom share screen) access to review de-identified data to other investigators to support analyses. Further, screening and enrollment data will be shared with the National Institute on Aging, the study's funder, which requires these data to be uploaded as a part of their CROMS requirements on a monthly basis:  
<https://www.nia.nih.gov/research/grants-funding/nias-clinical-research-operations-management-system-croms>

[Data sharing with NeuViCare: Identifiable information about participants will be shared with the NeuViCare app to administer the CONFIDENCE study. With the participant's consent, we will add their email and phone number to register them for the CONFIDENCE app. We will also add their preferred topics on financial well-being in order to send tailored text messages. This information will be drawn from the baseline survey and Eventbrite registration, and will be entered directly into the NeuViCare app. The research team will also be able to view the app participant's completion of activities.](#)

[Data sharing with USC Family Consultants: In order to administer the CONFIDENCE program to caregivers, we will share the names, email addresses, and phone numbers of eligible caregivers with the USC Family Consultants. Family consultants will receive an affiliate ID at Case Western to receive emails about participant information, and to deliver sessions using at Case Western HIPAA-compliant Zoom account. Recordings for fidelity monitoring and attendance reports will be stored in a Case Western Box folder.](#)

- Describe how data will be sent: De-identified data will be shared by email

Contact information to use the app will be entered directly into the app

Affiliate accounts will be set up for USC Family Consultants to receive names by email, and for them to store recordings and attendance information in Boxl

No  
 N/A

*If sharing data, please complete a request to ensure the proper contracts/agreements are in place: <https://case.edu/research/faculty-staff/technology-transfer/material-transfer-data-use-agreements>*

## 18.0 HIPAA Authorization

Does this study collect, access, use, or distribute any Protected Health Information (PHI)?  
*Protected Health Information (PHI) is (1) any individually identifiable health information transmitted or maintained in a medical record, paper or electronic, or (2) designated data set that was created, disclosed, or used in the course of providing a health care service such as diagnosis, payment or treatment.*

Yes       No

If yes, indicate how HIPAA authorization will be obtained (check all that apply):

HIPAA authorization is in the consent form  
 I am receiving a Limited Data Set under a Data Use Agreement (DUA)  
 Requesting a full or partial waiver of HIPAA for prescreening  
 I will complete the Request for Waiver of HIPAA Authorization form. *See SpartaIRB Library*  
 Requesting a full or partial waiver of HIPAA  
 I will complete the Request for Waiver of HIPAA Authorization form. *See SpartaIRB Library*

## 19.0 FERPA Authorization

Does this study collect, access, use, or distribute any personally identifiable information from student records or personal education information from an education program (defined as: any program principally engaged in the provision of education, including, but not limited to, early childhood education, elementary and secondary education, postsecondary education, special education, job training, career and technical education, and adult education)? This includes, but is not limited to, classroom assignments and course evaluations.

Yes       No

If yes, how do you plan to get written authorization from the student (or parent if the student is a minor)?

- I will incorporate FERPA language\* into the consent and obtain written and dated signature or authorized electronic signature using REDCap
- I will incorporate FERPA language\* into a separate form and obtain written and dated signature or authorized electronic signature using REDCap

## 20.0 Risks to Research Participants

1. List the reasonably foreseeable risks such as breach of confidentiality, discomforts, hazards, or inconveniences to the research participants related to their participation in the research. Include a description of the probability, magnitude, duration, and reversibility of the risks. Include the physical psychological, social, legal, and economic risks.
 

Breach of confidentiality. This is unlikely to occur, as all the research data collected will be de-identified and each participant will be assigned a different ID that only the PI will have access to. Emotional distress, such as finding intervention activities and survey questions uncomfortable or upsetting is also unlikely but possible. Participants will be reminded that participation is voluntary in each moment, and survey questions can be chosen to be skipped. Finally, there is a slight possibility that participants would receive information that is incorrect for their individual situations while using the NeuViCare app. The most likely outcome, if this occurs, is inconvenience, such as applying for a financial aid program that is not relevant to the caregiver. It would be unlikely that a caregiver would receive information that would harm them financially, given that all sources from which the AI responses will be drawn are either hand-picked (e.g., Department of Labor's information on Family Medical Leave) or developed by the research team. Further, multiple elder law professionals were involved in generating or reviewing intervention materials. However, we include language in the consent form notifying participants of this possibility.
2. If applicable, indicate which experimental procedures may have risks to the research participants that are currently unforeseeable. We cannot identify any unforeseeable risks to participation
  - N/A
3. If applicable, describe the risks to others who are not research participants. Click here to enter text.
  - N/A
4. Describe the availability of medical or psychological resources that research participants might need. As a part of the CONFIDENCE intervention, participants are provided with multiple resources to help with caregiving, including information about how to access counseling, support groups, and respite care for caregiver stress
  - N/A

## 21.0 Provisions to Protect the Privacy Interests of Research Participants

\* FERPA language: 1. Specify the educational records that may be both accessed and used in the research. 2. State the purpose of the access and use of records. 3. Identify to whom the records disclosure may be made.

**Directions: Indicate the measures that will be taken to protect research participants' privacy interests. Select all that apply:**

- In person interactions will be conducted in a private space where conversations would not be overheard by others -- this could be at a specific location determined by the research team or at a location that the participant chooses.
- For online/remote data collection, participants will be advised to choose a location that would be private.
- Researchers will only contact participants if permission has been given to do so.
- Other: Participants will be notified both during an initial telephone call, in the consent form, and when registering for the NeuViCare app that their information, including inquiries submitted to "Keiko" will be stored for the purpose of evaluation. These reminders are intended to prevent caregivers from providing personal information they would not wish to share when communicating with the AI assistant. Even if this does occur, these entries will be reported in aggregate and will not be linked to individual participants.

## 22.0 Potential Benefit to Research Participants

- There is potential benefit to research participants.

Describe the potential benefits that individual research participants may experience from taking part in the research. Include the probability, magnitude, and duration of the potential benefits. *Do not list compensation.* Participants will learn about resources on how to reduce caregiving costs (e.g., reduced cost home modifications) and they may discuss challenges experienced with other caregivers, which could be therapeutic.

- There is no direct benefit to research participants.

If no direct benefit, state the potential benefit to society or others. *Do not list compensation.* [Click here to enter text.](#)

## 23.0 Withdrawal of Research Participants

**Directions: Describe the anticipated circumstances under which research participants will be withdrawn from the research without their consent. Also include the procedures that will be followed when a research participant withdraws or are withdrawn from the research, including partial withdrawal from procedures with continued data collection.**

Participants will be removed from the study if the study team believes the participant is fraudulent (e.g., inconsistencies in study information provided), submits surveys that are excessively incomplete (e.g., more than 50% of responses are missing), or is no longer eligible (e.g., care recipient passes away). Participants will be notified by email if they are removed from the study. Participants may continue to participate in the study to complete the second follow up survey, even if the first follow up survey is not complete. The research team will retain study data for participants who are withdrawn or lost to follow up, unless it is specifically requested by the participant that data be removed prior to de-identification.

- N/A

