## 2.0 Objectives

**Directions: Describe the purpose, specific aims or objectives. Be sure to also include the hypothesis being tested.** The overall objective of this project is to test the feasibility, acceptability, and preliminary efficacy on an AI-enhanced psychoeducational intervention to reduce financial strain among Latino/Hispanic family caregivers to people living with dementia (PLWD) by supporting resource access called CONFIDENCE 2. The central hypothesis is that caregivers who participate in the CONFIDENCE intervention will report higher levels of resourcefulness and self-efficacy following participation in the CONFIDENCE intervention that will reduce financial strain among caregivers of PLWD.

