## 4.0 Inclusion and Exclusion Criteria

**Directions: Describe how individuals will be screened for eligibility.**

Participants will be asked to either complete an online self-administered survey to determine their eligibility, or to complete eligibility questions by telephone.

**Using the tables below, describe the inclusion and exclusion criteria that will define who will be included and excluded in your final study sample.**

Inclusion	
1.	Age range: from 18 to not upper limit
2.	Has been at least 6 months since the care recipient began to experience dementia symptoms
3.	Person living with dementia meets stage 4 to 6 criteria on Global Deterioration Scale according to family caregiver
4.	Latino/Hispanic ethnicity

Exclusion	
1.	Individuals who plan to place their family member in a nursing home in the next 3 months
2.	Unreliable access to internet, tablet or smart phone, and email
3.	Does not agree to participate in at least 3 of the 4 group sessions and/or register for the NeuViCare app
4.	Unable to read and speak in English or Spanish

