**Recruitment strategy.** Caregivers will primarily be recruited from the USC FCSC by sending information about CONFIDENCE via email blast, as well as individual email invitations and follow-up calls sent to participants who are likely to be eligible for the study. The USC FCSC may also advertise this program via social media channels and with community partners, as they would any program they offer to the community. Caregivers may also learn about the study on the Alzheimer’s Association TrialMatch

site.

**Enrollment and consenting.** Participants who register on Eventbrite and are interested in learning about the study will receive up to four calls and emails by a study team member to learn more about the study. If interested in participating, eligibility screening and a review of the study consent information will be conducted by phone with the PI or a trained study team member. (Participants may complete the screening process online, but are asked to complete a telephone follow up where they will be asked the screening item about the Global Deterioration Scale and other questions they did not respond to.) Participants will then be sent an email with a REDCap consent form to review and signature. Total enrollment and consenting time is estimated to take up to 1 hour.

**Survey administration.** Once enrolled, participants will receive the baseline survey up to 3 weeks before their first CONFIDENCE session by email, which includes questions about spending on out-of-pocket care costs, financial strain, resourcefulness, self-efficacy, and information about the caregiving context and use of supports. The first follow-up survey will be sent immediately post-intervention (i.e., within 1 week). A second follow-up survey will be sent two months following intervention completion to understand the maintenance of outcomes. We estimate follow up surveys take about 30 to 45 minutes to complete.

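### Section 23 removes caregivers who stop meeting the entry criteria, yet two of those criteria can change as dementia runs its course, so follow-up can be lost for outcome-related reasons

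*Combined protocol and SAP*

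**What the plan says.** Section 23.0 (Withdrawal of Research Participants) lists grounds on which the team removes a participant: suspected fraud, surveys that are largely incomplete, and a third ground worded "or is no longer eligible (e.g., care recipient passes away". It does not say which criteria are meant, who re-checks them, or when.

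Section 4.0 has two criteria that depend on the care recipient's course:

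- Inclusion: "Person living with dementia meets stage 4 to 6 criteria on Global Deterioration Scale according to family caregiver".
- Exclusion: "Individuals who plan to place their family member in a nursing home in the next 3 months".

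On follow-up, Section 12.0 (Survey administration) says "A second follow-up survey will be sent two months following intervention completion to understand the maintenance of outcomes". On what happens to removed participants, Section 23.0 says "The research team will retain study data for participants who are withdrawn or lost to follow up", unless the participant asks otherwise. It also says "Participants may continue to participate in the study to complete the second follow up survey, even if the first follow up survey is not complete". It does not say whether a removed caregiver is still sent surveys.

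Section 17.0 compares baseline with each follow-up by t-test. It names no analysis set, no missing-data rule and no denominator for attendance.

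**The concern.** An entry criterion defines who starts. Carried forward as a reason for removal, it makes staying in the study depend on what happens after the start. Here, what happens after the start includes the progression of dementia and the decision to seek placement. Both are plausibly related to caregiving costs, financial strain (a secondary outcome) and self-efficacy (the second primary outcome).

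The design has no control arm, so selective loss goes straight into the estimated change. A comparison group that might lose similar caregivers does not exist. Section 17.0 has no analysis rule that would deal with the loss, and a survey that was never sent cannot be recovered later. Because the scope of the rule is open, staff would also have to decide case by case. Section 28.0 has surveys reviewed within a week of completion, so such a decision could follow sight of the answers.

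**Working it through.** **1. Does the observation period outlast the placement horizon?** Inputs: baseline survey up to 3 weeks before the first session (Sections 8.0 and 12.0); programme of 4 weeks (Section 12.0), or 4 to 5 weeks per cohort (Section 8.0); second follow-up 2 months after completion (Section 12.0), taken as 8.7 weeks.

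- Shortest: 0 + 4 + 8.7 = 12.7 weeks.
- Longest: 3 + 5 + 8.7 = 16.7 weeks.
- Placement horizon in Section 4.0: 3 months = 13.0 weeks.

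The two overlap, and screening comes before baseline, so the real interval is somewhat longer. The horizon also rolls forward if the criterion is re-applied. A caregiver who at screening plans placement in 4 months (an assumed example) is eligible. One month later the same plan is 4 − 1 = 3 months away and meets the exclusion, although nothing has changed.

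**2. How large could the effect be?** The plan gives no number removed, no SD of change and no effect size, so what follows is illustration. Its only related figures are 42 recruited and 20% attrition (Section 5.0). Since 42 × 0.80 = 33.6, I take 33 completers as the base. The figure 42 cannot be uniquely reproduced, because no evaluable target is stated: 33 / 0.80 = 41.25 rounds up to 42, and 35 × 1.20 is also 42.

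If a share r is removed, and those kept differ from those removed by D (in SDs of change), the mean among those kept differs from the mean in all by r × D.

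- r = 0.05, D = 0.25: 0.05 × 0.25 = 0.0125, about 0.01 SD.
- r = 0.30, D = 1.0: 0.30 × 1.0 = 0.30 SD.

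Precision also falls. For a paired t-test (two-sided 0.05, 80% power) the detectable change is 0.50 SD at n = 33. It is 0.52 SD at n = 31 (5% removed) and 0.61 SD at n = 23 (30% removed).

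**3. Which way would it go?** Assume 34 caregivers kept, with a mean improvement of 2 points on the COST scale (range 0 to 44), and 3 removed.

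- The 3 worsen by 10: (34 × 2 − 3 × 10) / 37 = 38 / 37 = 1.03. The observed 2.0 is too high.
- The 3 improve by 10: (34 × 2 + 3 × 10) / 37 = 98 / 37 = 2.65. The observed 2.0 is too low.

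Three caregivers can matter either way. The 10-point changes are deliberately large, and the documents support neither sign.

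**The case against.** The strongest reply is that removal for progression or placement is a possible reading and not a stated practice. Death is the only example given. Section 12.0 treats the dementia-stage item as a screening question and describes no reassessment. Actual placement is not a listed exclusion; only a plan to place is. All of this is correct, and the rule may seldom be used in this way. But removal is worded as mandatory and without limit, so the text permits that use and does not tell staff where to stop.

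A second reply is that data are retained and that a missed first follow-up does not end participation. This protects what has already been collected. It does not say that later surveys are sent to someone who has been removed.

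A reader might also infer that the rule removes low attenders and so inflates the feasibility result. The documents do not support that. The criterion reads "Does not agree to participate in at least 3 of the 4 group sessions and/or register for the NeuViCare app". It concerns agreement at entry, and nothing says that it is asked again. Facilitators record attendance independently of the surveys (Section 12.0), it is reported over 0 to 4 sessions (Section 17.0), and withdrawn participants' data are kept. No passage drops removed caregivers from the attendance or retention counts. What remains is that the denominators are unstated, in a study meant to "test the feasibility, acceptability, and preliminary efficacy".

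**Conclusion.** The point stands for dementia stage and placement plans. Read literally, Section 23.0 ends follow-up for caregivers whose situation changed, and the single-arm pre-post comparison has no rule for handling that loss. The timing rests on figures in the plan. The range of 0.01 to 0.30 SD rests wholly on the assumed removal shares and outcome differences, and shows only that the effect could run from negligible to material.

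A reader might conclude that the change in strain would look better than it was. That does not follow. Section 3.0 links intensive care at home to disrupted employment and higher out-of-pocket costs, so placement could lower strain as well as raise it. The direction is unknown. The amendment is nonetheless worth making, because it removes an avoidable source of selective loss at little cost.

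**What to change.** In Section 23.0, state that eligibility is judged once, at enrolment, and limit later removal on eligibility grounds to the example already given, death of the care recipient. State that caregivers whose relative progresses, is placed or is planned for placement continue to receive both follow-up surveys.

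In Section 17.0, state that these caregivers stay in the outcome analysis, and that all enrolled caregivers, including any who are removed, stay in the attendance and retention denominators.

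Optionally, record placement at each follow-up and show the outcome change with and without those caregivers.

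The cost is a short amendment and, per caregiver kept, at most $50 + $60 = $110 in follow-up payments (Section 26.0). The small downside is that some follow-up surveys will come from caregivers in a changed situation. The optional step adds one survey question and one table.
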